5.2.4 Non-target lesions

All other lesions (or sites of disease) including any measurable lesions over and above the 5 target lesions should be identified as **non-target lesions** and should also be recorded at baseline. Measurements of these lesions are not required, but the presence, absence, or in rare cases unequivocal progression of each should be noted throughout follow-up.

5.3 Methods for Evaluation of Measurable Disease

All measurements should be taken and recorded in metric notation using a ruler or calipers. All baseline evaluations should be performed as closely as possible to the beginning of treatment and never more than 28 days before the beginning of the treatment.

The same method of assessment and the same technique should be used to characterize each identified and reported lesion at baseline and during follow-up. Imaging-based evaluation is preferred to evaluation by clinical examination when both methods have been used to assess the antitumor effect of a treatment.

5.3.1 Clinical lesions

Clinical lesions will only be considered measurable when they are ≥ 10 mm diameter. For superficial lesions measured by caliper, documentation by color photography including a ruler in the field of view is strongly recommended.

5.3.2 Chest x-ray

Lesions on chest x-ray are acceptable as measurable lesions when they are clearly defined and surrounded by aerated lung. However, CT is preferable.

5.3.3 Conventional CT and MRI

This guideline has defined measurability of lesions on CT scan based on the assumption that CT slice thickness is 5 mm or less. If CT scans have slice thickness greater than 5 mm, the minimum size for a measurable lesion should be twice the slice thickness. MRI is also acceptable in certain situations (e.g. for body scans), but NOT lung.

Use of MRI remains a complex issue. MRI has excellent contrast, spatial, and temporal resolution; however, there are many image acquisition variables

involved in MRI, which greatly impact image quality, lesion conspicuity, and measurement. Furthermore, the availability of MRI is variable globally. As with CT, if an MRI is performed, the technical specifications of the scanning sequences used should be optimized for the evaluation of the type and site of disease. Furthermore, as with CT, the modality used at follow-up should be the same as was used at baseline, and the lesions should be measured/assessed on the same pulse sequence. It is beyond the scope of the RECIST guidelines to prescribe specific MRI pulse sequence parameters for all scanners, body parts, and diseases. Ideally, subsequent image acquisitions should use the same type of scanner and follow the baseline imaging protocol as closely as possible. If possible, body scans should be performed with breath-hold scanning techniques.

5.3.4 PET-CT

At present, the low dose or attenuation correction CT portion of a combined PET-CT is not always of optimal diagnostic CT quality for use with RECIST measurements. PET-CT scans are not always done with oral and IV contrast. In addition, the PET portion of the CT introduces additional data that may bias an investigator if it is not routinely or serially performed. For these reasons, we will not allow PET-CT use for RECIST 1.1 response criteria.

5.3.5 FDG-PET

While FDG-PET response assessments need additional study, it is sometimes reasonable to incorporate the use of FDG-PET scanning to complement CT scanning in assessment of progression (particularly possible "new" disease). New lesions on the basis of FDG-PET imaging can be identified according to the following algorithm:

- Negative FDG-PET at baseline, with a positive FDG-PET at follow-up is a sign of PD based on a new lesion.
- No FDG-PET at baseline and a positive FDG-PET at follow-up: If the positive FDG-PET at follow-up corresponds to a new site of disease confirmed by CT, this is PD. If the positive FDG-PET at follow-up is not confirmed as a new site of disease on CT, additional follow-up CT scans are needed to determine if there is truly progression occurring at that site (if so, the date of PD will be the date of the initial abnormal FDG-PET scan). If the positive FDG-PET at follow-up corresponds to a pre-existing site of disease on CT that is not progressing on the basis of the anatomic images, this is not PD.

Note: A "positive" FDG-PET scan lesion means one that is FDG avid with an uptake greater than twice that of the surrounding tissue on the attenuation corrected image.

5.3.6 Ultrasound

Ultrasound is not useful in assessment of lesion size and should not be used as a method of measurement. Ultrasound examinations cannot be reproduced in their

entirety for independent review at a later date and, because they are operator dependent, it cannot be guaranteed that the same technique and measurements will be taken from one assessment to the next. If new lesions are identified by ultrasound in the course of the study, confirmation by CT or MRI is advised. If there is concern about radiation exposure at CT, MRI may be used instead of CT in selected instances.

5.3.7 Endoscopy, Laparoscopy

The utilization of these techniques for objective tumor evaluation is not advised. However, such techniques may be useful to confirm complete pathological response when biopsies are obtained or to determine relapse in trials where recurrence following complete response (CR) or surgical resection is an endpoint.

5.3.8 CA-125 (Ovarian, fallopian tube and primary peritoneal cancer trials) If CA125 is initially above the upper normal limit then it may be used as a marker of treatment efficacy. It must normalize for a patient to be considered in complete clinical response. Specific guidelines for CA-125 response (in recurrent ovarian cancer) have been published [15]. In addition, the Gynecologic Cancer Intergroup has developed CA-125 progression criteria that are to be integrated with objective tumor assessment for use only in first-line trials in ovarian cancer [17]. See section 5.4.3 for explanation of clinical response.

5.3.9 Cytology, Histology

These techniques can be used to differentiate between partial responses (PR) and complete responses (CR) in rare cases, e.g., residual lesions in tumor types, such as germ cell tumors, where known residual benign tumors can remain.

It is mandatory to obtain cytological confirmation of the neoplastic origin of any effusion that appears or worsens during treatment when measurable disease has met criteria for response or stable disease. This confirmation is necessary to differentiate response or stable disease versus progressive disease, as an effusion may be a side effect of the treatment.

5.4 Response Criteria

Determination of response should take into consideration all target and non-target lesions and, if appropriate, biomarkers.

5.4.1 Evaluation of Target Lesions

Complete Response (CR): Disappearance of all target lesions. Any pathological lymph nodes (whether target or non-target) must have reduction in short axis to <10 mm.

Partial Response (PR): At least a 30% decrease in the sum of the diameters of target lesions, taking as reference the baseline sum diameters.

Progressive Disease (PD): At least a 20% increase in the sum of the diameters of target lesions, taking as reference the smallest sum on study (this includes the

baseline sum if that is the smallest on study). In addition to the relative increase of 20%, the sum must also demonstrate an absolute increase of at least 5 mm. (Note: the appearance of one or more new lesions is also considered progressions).

Stable Disease (SD): Neither sufficient shrinkage to qualify for PR nor sufficient increase to qualify for PD, taking as reference the smallest sum diameters while on study.

5.4.2 Evaluation of Non-Target Lesions

Complete Response (CR): Disappearance of all non-target lesions. All lymph nodes must be non-pathological in size (<10 mm short axis).

Note: If CA-125 is initially above the upper normal limit, it must normalize for a patient to be considered in complete clinical response.

Non-CR/Non-PD: Persistence of one or more non-target lesion(s)

Progressive Disease (PD): Appearance of one or more new lesions and/or unequivocal progression of existing non-target lesions. Unequivocal progression should not normally trump target lesion status. It must be representative of overall disease status change, not a single lesion increase.

Not evaluable (NE): When at least one non-target lesion is not evaluated at a particular time point.

Although a clear progression of only 'non-target' lesions is exceptional, the opinion of the treating physician should prevail in such circumstances, and the progression status should be confirmed at a later time by the review panel (or Principal Investigator).

5.4.3 Evaluation of Biomarkers

If serum CA-125 is initially above the upper normal limit, it must normalize for a patient to be considered in complete clinical response. A partial response according to CA 125 has occurred if there is at least a 50% reduction in CA 125 levels from a pretreatment sample but the value remains above the normal range. The response must be confirmed and maintained for at least 28 days. A complete response has occurred if the CA-125 level decreases into the normal range. Progressive disease will be defined as a doubling of CA-125 levels. Stable disease will be any CA-125 level that falls within the range of progressive disease and partial response.

5.5 **Duration of Response**

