2 STUDY OBJECTIVES

2.1 Primary

The primary objective of this single-arm, phase II clinical trial will be to determine the clinical activity of tivozanib in patients with platinum-resistant, recurrent ovarian, fallopian tube or primary peritoneal cancer. For this protocol text, these disease entities will be referred to collectively as ovarian cancer. The primary endpoint of this trial will be the overall response rate of patients with platinum-resistant ovarian cancer to treatment with single agent tivozanib as measured by physical exam findings, serum CA-125 levels and/or measurement of index lesions via appropriate imaging studies using RECIST criteria.

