3 PATIENT SELECTION

The target population for this study is patients with recurrent or persistent, platinum resistant epithelial ovarian, fallopian tube or primary peritoneal carcinoma. This will be a multicenter trial conducted at Northwestern Medicine. Northwestern University will serve as the lead site and coordinating center for this study. Participating sites will include Northwestern Medicine Cancer Center Warrenville and the Northwestern Medicine Cancer Center Delnor and Northwestern Lake Forest Hospital.

A total of 30 subjects will be needed for this trial. Approximately 6 potentially eligible patients are seen per month, and it is anticipated that at least 3 per month will be accrued (once all sites are up and running). Potential patients may be referred to the Principal Investigator (PI) at Northwestern University, [name], at [contact], or to the local PI at each participating site.

Eligibility will be evaluated by the study team according to the following criteria. Eligibility waivers are not permitted. Subjects must meet all of the inclusion and none of the exclusion criteria to be registered to the study. Study treatment may not begin until a subject is registered. Please refer to Section 10 for complete instructions regarding registration procedures.

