3.1 Inclusion Criteria

Each patient must meet all of the following inclusion criteria to be enrolled in the study:

- 3.1.1 Patients must have recurrent or persistent, platinum resistant or refractory epithelial ovarian, fallopian tube or primary peritoneal carcinoma. Platinum-resistant disease is defined as a recurrence within 6 months of completing platinum-based chemotherapy.
- 3.1.2 Patients must have measurable disease or non-measurable (detectable) disease:
 - Measurable disease is defined as at least one lesion that can be accurately measured in at least one dimension (longest diameter to be recorded). Each lesion must be greater than or equal to 10 mm when measured by CT, MRI or by clinical exam; or greater than or equal to 20 mm when measured by chest x-ray. Lymph nodes must be greater than or equal to 15 mm in short axis when measured by CT or MRI.

- Non-measurable (detectable) disease in a patient is defined in this protocol as one who does not have measurable disease based on RECIST criteria but does have a CA-125 greater than or equal to two times the upper normal limit within the last 60 days (confirmatory at baseline) and at least one of the following conditions:
 - Ascites and/or pleural effusion attributed to tumor
 - Hypermetabolic lesions on PET Scan
- 3.1.3 Patients with measurable disease must have at least one target lesion as defined by RECIST 1.1 to be used to assess response on this protocol.
- 3.1.4 Patients must have an ECOG Performance Status of 0, 1, or 2.
- 3.1.5 Patients must have had one prior taxane and platinum-based chemotherapeutic regimen for management of primary disease containing carboplatin, cisplatin, or another organoplatinum compound. This initial treatment may have included intraperitoneal therapy, consolidation, non-cytotoxic (biologic/targeted agents) or extended therapy administered after surgical or non-surgical assessment. There is no maximum number of prior regimens.

Note: Use of bevacizumab as maintenance therapy after initial adjuvant platinumbased chemotherapy is allowed so long as platinum-resistant recurrence occurred subsequent to a separate platinum-based regimen AND more than 6 months after completion of bevacizumab maintenance.

- 3.1.6 Patients must have signed an approved informed consent and authorization permitting the release of personal health information.
- 3.1.7 Patients must be willing and able to complete all study procedures.

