5.1 Antitumor Effect – Solid Tumors

Response and progression will be evaluated in this study using the international criteria proposed by the revised Response Evaluation Criteria in Solid Tumors (RECIST) guideline (version 1.1) [16]. Changes in the largest diameter (unidimensional measurement) of the tumor lesions and the shortest diameter in the case of malignant lymph nodes are used in the RECIST criteria.

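### Section 5.4.3 allows a CA-125 complete response after a smaller fall than a partial response needs, and no section says how a CA-125 response without a RECIST response enters the 4-of-30 count

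*Combined protocol and SAP*

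**What the plan says.** The primary endpoint in section 2.1 is the overall response rate "as measured by physical exam findings, serum CA-125 levels and/or measurement of index lesions via appropriate imaging studies using RECIST criteria". The introduction to section 5 lists the same three sources and calls for imaging where the disease state indicates it. Section 5.1 reads differently: "Response and progression will be evaluated in this study using the international criteria proposed by the revised Response Evaluation Criteria in Solid Tumors" (version 1.1). Section 5.4 says that all lesions are to be considered, and biomarkers where appropriate.

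On the marker, section 5.3.8 says "If CA125 is initially above the upper normal limit then it may be used as a marker of treatment efficacy" and then "See section 5.4.3 for explanation of clinical response". Section 5.4.3 gives four CA-125 categories:
- partial response: a fall of at least 50% with the value still above normal, confirmed and maintained for 28 days;
- complete response, in the sentence after the 28-day requirement: "A complete response has occurred if the CA-125 level decreases into the normal range";
- progression: a doubling;
- stable disease: anything between progression and partial response.

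Sections 5.3.8, 5.4.2 and the opening of 5.4.3 also make normalisation a necessary condition for complete clinical response.

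Under 3.1.2, a patient with only non-measurable disease must be one who "does have a CA-125 greater than or equal to two times the upper normal limit within the last 60 days", confirmed at baseline. No CA-125 minimum applies to measurable disease.

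Footnote 11 of the schedule in 7.1 requires confirmation of CR and PR at 4 weeks or more and refers to Section 8, which has no such rule. Section 8 counts CR or PR using examination, CA-125 and imaging. It stops the trial at 0 responses in the first 10 patients and rejects the 5% null at 4 or more in 30. It also records that the monitoring committee reviewed the first 9 evaluable patients on 10/12/16 and opened the study to 21 more.

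**The concern.** There are two separate defects.

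First, the better category is easier to reach than the worse one for some patients. The complete-response sentence has no minimum fall, so a change within the stable-disease range also qualifies as a CA-125 complete response if it crosses the upper limit of normal.

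Second, the plan has no rule for combining sources. If any one source suffices, as the and/or in 2.1 allows, a CA-125 response with RECIST stable disease is a responder. If RECIST governs, as 5.1 suggests, it is not. Two people applying the text in good faith can count the same patient differently. Patients with only non-measurable disease are in the same position: without a complete response or progression, 5.4.2 can class them only as Non-CR/Non-PD, and it has no partial response.

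The primary conclusion depends on a cut-off of 4 patients, so one such classification can settle it. A smaller point affects progression-free survival: the text does not make clear whether a CA-125 doubling alone is an event, or from which value the doubling is measured.

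**Working it through.** **1. Where the missing floor matters.** Let the baseline be b × ULN. The smallest fall that reaches ULN is 1 − 1/b.

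| Baseline (× ULN) | Fall needed to reach ULN |
|---|---|
| 1.1 | 9.1% |
| 1.25 | 20.0% |
| 1.5 | 33.3% |
| 1.75 | 42.9% |
| 2.0 | 50.0% |

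Only baselines between 1 and 2 × ULN escape the 50% threshold. Example: 1.1 to 0.95 × ULN is 1 − 0.95/1.1 = 13.6%, which meets the complete-response sentence and also lies in the stable-disease range. By contrast, 10 to 5.1 × ULN is 1 − 5.1/10 = 49%, which is stable disease only. Patients with only non-measurable disease enter at 2 × ULN or more, so the gap does not reach them if the baseline sample confirms that level.

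**2. The plan's own design figures.** Inputs from Section 8: 10 + 20 patients, stop at 0 responses in stage 1, reject at 4 or more of 30, null rate 5%, alternative 20%. With X₁ and X₂ the responses in each stage, the exact probability of rejection is

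Σ (x = 1 to 10) P(X₁ = x) × P(X₂ ≥ 4 − x).

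This gives 0.0513 at 5% and 0.8141 at 20%, against the stated 5% type I error and 80% power. The recorded 9 + 21 split gives 0.0489 and 0.7928.

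**3. One disputed stage-2 patient.** Fix that patient as a responder (d = 1) or non-responder (d = 0). The other 29 respond independently at rate p, so stage 2 has 19 other patients under 10 + 20:

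Σ (x ≥ 1) P(X₁ = x) × P(X₂ ≥ 4 − d − x), with X₂ binomial on 19.

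At p = 0.05, P(X₁ = 1, 2, 3) = 0.3151, 0.0746, 0.0105.
- d = 0: 0.3151 × 0.0665 + 0.0746 × 0.2453 + 0.0105 × 0.6226 + 0.0010 = 0.0468.
- d = 1: 0.3151 × 0.2453 + 0.0746 × 0.6226 + 0.0115 = 0.1353.

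| Split | p for other 29 | Not counted | Counted |
|---|---|---|---|
| 10 + 20 | 5% | 4.7% | 13.5% |
| 9 + 21 | 5% | 4.5% | 12.8% |
| 10 + 20 | 20% | 80.1% | 86.6% |
| 9 + 21 | 20% | 78.1% | 84.1% |

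**4. At the boundary.** Clopper-Pearson one-sided 95% lower limits: 3/30 = 10.0%, limit 2.8%, null not rejected; 4/30 = 13.3%, limit 4.7%, null rejected under the rule. The limit at 4/30 is still just under 5%, so it is the counting rule that decides.

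**5. Draw timing.** Footnote 15 allows the CA-125 draw up to 14 days before each 28-day cycle, and the schedule has none at end of treatment. A draw on day 1 and the next one 14 days before the following cycle are 28 − 14 = 14 days apart, too close for a 28-day confirmation.

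**The case against.** The strongest reply is that the complete-response sentence defines a marker category, not an overall response. It stands under biomarker evaluation, and 5.4.3 opens by making normalisation a requirement for complete clinical response. Sections 5.4.1 and 5.4.2 require all lesions to disappear for CR and treat a new lesion as progression. Much of this stands. A reader might infer that the protocol would score normalisation as an overall CR while lesions persist or progress. The documents weigh against that, although none rules it out expressly. The reply does not say how a marker response with RECIST stable disease is counted.

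A reader might also infer that CA-125 responses need no confirmation. That is not supported: footnote 11 requires it for CR and PR without limiting it to imaging. What remains is its place in an imaging footnote, a reference to a rule that Section 8 lacks, and sentence order in 5.4.3.

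A third tempting inference is a definite contradiction on progression. Section 5.3.8 says that an intergroup has "developed CA-125 progression criteria that are to be integrated with objective tumor assessment for use only in first-line trials in ovarian cancer", whereas here "The target population for this study is patients with recurrent or persistent, platinum resistant epithelial ovarian, fallopian tube or primary peritoneal carcinoma". But 5.3.8 describes another group's criteria, while 5.4.3 sets the protocol's own doubling rule. The text is unclear but does not show a definite conflict.

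Finally, any cut-off can be crossed by one patient, and such a patient may not exist. That is true, and it limits the size of the claim. It does not supply the missing rule.

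**Conclusion.** The point holds in two parts. The CA-125 complete-response sentence is defective as written for patients with measurable disease and a baseline between 1 and 2 × ULN. The first part changes the primary count only if such a patient has no RECIST response and the CA-125 result is then counted. The second part is broader: for any CA-125 response without a RECIST response, including in patients with only non-measurable disease, the plan gives no rule and its two natural readings disagree.

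The size is conditional. If one such patient is in stage 2, the chance of meeting the rule with the others at 5% is 4.7% or 13.5% (10 + 20), or 4.5% or 12.8% (9 + 21). This assumes independent responses and exactly one disputed patient. It is not an estimate of the trial's type I error. That would need a discordance rate, which the documents do not give, and a statement that the 5% null is a RECIST rate, which they do not make. The matter should be fixed before final response classification.

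**What to change.** 1. **Section 5.4.3.** Require a CA-125 complete response to meet the same fall of at least 50% and the same 28-day confirmation as a CA-125 partial response. State that the confirmation rule in footnote 11 covers CA-125 responses, and put that rule in Section 8.
2. **Section 5.4 and Section 8.** State that normalisation alone is not an overall CR while lesions persist, and that RECIST progression or a new lesion on or before the confirmation date overrides a CA-125 response. Fix one rule for a CA-125 response with RECIST stable disease, and one for patients with only non-measurable disease, before final classification. Either choice for stable disease can be defended from the text, so the team should choose and give its reason.
3. **Reporting.** Whichever rule is chosen, give the count with and without CA-125-only responses, the RECIST 1.1 response rate in measurable disease, and the number of CA-125-only responders. Present neither count as the one the protocol always meant. State that the change follows the 10/12/16 interim review.
4. **Progression.** Reconcile 5.3.8 and 5.4.3 by stating whether a CA-125 doubling is a progression-free-survival event in this trial and, if so, from which reference value.

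The cost is a dated amendment, a re-read of the CA-125 and imaging records for all patients, and one more response table. The response rate may come out slightly lower, and some CA-125 responses may stay unconfirmed because of the draw timing.
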